6.1 Toxicity criteria

This trial will assess only the grade 3 and 4 toxicities related to the Vitamin D administration. The NCI Common Toxicity Criteria Adverse Events (CTCAE) Version 4 (Appendix B) will be used to grade toxicity. It is available at the following internet site:

http://ctep.cancer.gov/protocolDevelopment/electronic_applications/ctc.htm#ctc_40

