6.2 Survival

Subjects will be analyzed with respect to overall and progression-free survival.

Overall survival is defined as time from study entry until death from any cause. For subjects who are still alive at the time of the study analysis or are lost to follow-up, survival will be censored at the last recorded date that the subject was known to be alive.

Progression-free survival is defined as time from study entry until the first notation of clinical progression, relapse, starting new therapies or death from any cause. For subjects who are still progression-free at the time of the study analysis or are lost to follow-up, progression-free will be censored at the last recorded date that the subject was known to be progression-free.

Response will be determined by the Principal Investigator or the lead site investigators.

Section 7.0 Study Parameters:

	Low Levels <30 ng/mL - RANDOMIZED GROUP					
	Pre-Treatment (within 30 days of Consent)	First Dose	6 months Day 182 (+/- 30 Days)	12 months Day 365 (+/- 30 Days)	Year 2 Day 730 (+/- 30 Days)	Year 3 Day 1095 (+/- 30 Days) End of Study
History & Physical	X					
Height, Weight, Vital Signs	X					
Monitor for Vitamin D related AEs			X	X	X	X
Serum Calcium	X					
Serum 25- hydroxyvitamin D [25(OH) D]	X		X	X	X	X
Vitamin D		X - Daily Dosing at Home for 3 years				
Long-term progression free survival and outcome ¹						X

Normal Level $\geq 30\text{ng/ml}$ - CONTROL GROUP*		
Followed only for long-term progression free survival and outcome. No further evaluation of serum 25-hydroxyvitamin D [25(OH) D] will be obtained. (NOTE: subjects currently taking Vitamin D supplements will be encouraged to continue their supplementation.)		
Required studies	Pre-Treatment (Within 30 days of Consent)	Year 3 - Day 1095 (+/- 180 Days) End of Study
History & Physical	X	
Height, Weight, Vital Signs	X	
Serum Calcium	X	
Serum 25-hydroxyvitamin D [25(OH) D]	X	
Long-term progression free survival and outcome ¹		X

¹ Progression defined as relapse, progression, or starting new therapies, or death

Section 8.0 Drug Formulation and Procurement (per UNMC Lexicomp Online):

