This product may adversely interact with certain health and medical conditions, other prescription and over-the-counter drugs, foods, or other dietary supplements. This product may be unsafe when used before surgery or other medical procedures. It is important to fully inform your doctor about the herbal, vitamins, mineral or any other supplements you are taking before any kind of surgery or medical procedure. With the exception of certain products that are generally recognized as safe in normal quantities, including use of folic acid and prenatal vitamins during pregnancy, this product has not been sufficiently studied to determine whether it is safe to use during pregnancy or nursing or by persons younger than 2 years of age.

Section 9.0 Toxicity Reporting Guidelines:

This protocol will comply with monitoring and adverse event reporting requirements of the UNMC/Fred & Pamela Buffett Cancer Center Data Monitoring plan. The protocol will adhere to the institutional and FDA guidelines for the toxicity reporting.

Grade 3 and 4 adverse events (AEs) related to the Vitamin D administration will be graded according to the National Cancer Institute Common Terminology, Criteria for Adverse Events (NCI-CTCAE), version 4.0, which can be accessed at the following URL.

http://ctep.cancer.gov/protocolDevelopment/electronic_applications/ctc.htm#ctc_40

The over the counter agent used in the protocol is commercially available with a well-characterized toxicity profile.

All subjects will be closely followed for grade 3 and 4 toxicity/adverse events related to the Vitamin D administration from the time that the first dose of study drug is administered and ending 30 days following the final therapy. Adverse events will be assessed by reports from subjects of Vitamin D related grade 3 or higher adverse events to their physician-investigators, standard laboratory results and by physical examinations. Vitamin D related Only **prescription** medication taken to relieve symptoms of the Vitamin D related AE will be recorded in addition to the outcome. All other/routine concomitant medications WILL NOT be recorded. Deaths occurring within 30 days of study treatment regardless of relationship will be reported to the UNMC DSMC. Only fatal AEs will be reported to the UNMC IRB per the IRB's policy and procedures.

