9.2.1 IRB Reporting

All Vitamin D related internal serious adverse events (SAEs) must be reported to the local IRB promptly per institutional human research protection program policies.

9.2.2 Fred & Pamela Buffett Cancer Center Data and Safety Monitoring Committee (DSMC) Reporting

All Vitamin D related adverse events grade 3 or higher (expected or unexpected) will be reported to the University of Nebraska Medical Center, Fred & Pamela Buffett Cancer Center Data and Safety Monitoring Committee (DSMC) in accordance with DSMC guidelines.

In its initial review, the DSMC will make a recommendation for the frequency of DSMC monitoring based on an assessment of risk associated with study-associated therapy, per the DSMC policy.

Detailed policy and procedures for this section may be reviewed at:

<http://www.unmc.edu/cancercenter/clinical/prms.html>

Attribution of AE: The likelihood of relationship of the AE to the study drugs will be determined by the investigator based on the following definitions:

- **Not Related:** The subject was not exposed to the study treatment or another cause is obvious.
- **Probably Not Related:** The AE is most likely explained by another cause, and the time of occurrence of the AE is not reasonably related to the study treatment.
- **Possibly Related:** Study treatment administration and AE occurrence reasonably related in time, and the AE is explained equally well by causes other than study treatment, or treatment administration and AE occurrence are not reasonably related in time, but the AE is not obviously a result of other causes.
- **Probably Related:** Study treatment administration and AE occurrence are reasonably related in time, and the AE is more likely explained by study treatment than by other mechanisms.
- **Definitely Related:** There occurrence and timing of the AE are clearly attributable to the study treatment.

Severity Grade of AE. The severity of events reported on the AE case report form will be determined by the principal investigator according the NCI Common Toxicity Criteria (CTC version 4.0). Copies of the AE report will be submitted to the IRB as indicated in Section 9.1.1.

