10.2.5 Safety

The incidence of adverse events (AEs) and serious adverse events (SAEs) will be described for the low dose and high dose groups and compared between groups using a Chi-square. The frequency of occurrence of overall toxicity, categorized by toxicity grades, will be described for the low dose and high dose groups and compared between groups using a Chi-square.

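### Section 10.2.5 plans overall adverse event and toxicity-by-grade comparisons, but the protocol systematically collects only vitamin D related events of grade 3 or above, related SAEs and 30-day deaths

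*Combined protocol and SAP*

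**What the plan says.** Section 10.2.5 (Safety) sets out two analyses. The first is "The incidence of adverse events (AEs) and serious adverse events (SAEs) will be described for the low dose and high dose groups"; the second is "The frequency of occurrence of overall toxicity, categorized by toxicity grades, will be described for the low dose and high dose groups". Both are to be compared between the dose groups by Chi-square. Neither sentence restricts events by grade or by relationship to vitamin D.

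The sections that govern collection are narrower:

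- Section 6.1: "This trial will assess only the grade 3 and 4 toxicities related to the Vitamin D administration".
- Section 9.0: "All subjects will be closely followed for grade 3 and 4 toxicity/adverse events related to the Vitamin D administration". The same paragraph then uses a different limit: "Adverse events will be assessed by reports from subjects of Vitamin D related grade 3 or higher adverse events to their physician-investigators".
- Section 7.0, schedule for the randomized group: the only adverse event row is "Monitor for Vitamin D related AEs", at 6 and 12 months and years 2 and 3.
- Section 9.2.2, on reports to the data and safety monitoring committee (DSMC): "All Vitamin D related adverse events grade 3 or higher (expected or unexpected) will be reported".

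Two provisions go further. Section 9.1.2 defines a related SAE without a grade limit, and Sections 9.0 and 9.2.1 require such events to be reported. Section 9.0 also sends deaths within 30 days of study treatment to the DSMC whatever their cause.

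On attribution, Section 9.2.2 states: "The likelihood of relationship of the AE to the study drugs will be determined by the investigator based on the following definitions".

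**The concern.** The analysis section describes a wider set of events than the trial sets out to record. If the report follows 10.2.5, tables headed as adverse event incidence and overall toxicity will hold only the related, mostly severe part. A reader would take low counts, or empty grade 1 and 2 rows, as evidence that events were rare when most such events were never sought. That matters because the comparison is between a higher and a lower dose, and the safety paragraph is where a reader looks for the cost of the higher one.

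The second concern is how an event enters the data. Relatedness is a condition of entry, and the person judging it appears to know the dose. A difference between arms could then come from attribution as well as from toxicity.

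**Working it through.** The documents state no safety figure, so there is none to reproduce. The check sets planned analysis against planned collection.

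**1. Event types against collection**

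- Related, grade 3 or 4: collected (6.1, 9.0).
- Related, grade 5: outside the wording of 6.1 and of one sentence in 9.0; inside another sentence of 9.0 and 9.2.2. Inconsistent, not absent.
- Related, grade 1 or 2, serious: reportable as a related SAE (9.1.2, 9.0, 9.2.1).
- Related, grade 1 or 2, not serious: no systematic collection.
- Unrelated, fatal within 30 days of study treatment: reported (9.0).
- Unrelated, non-fatal, any grade: no systematic collection.

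The analysis in 10.2.5, read as worded, needs every line. Two lines have no planned source.

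**2. Direction and unit of the error**

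Let *A* be the patients in an arm with any adverse event and *C* those with at least one collected event. *C* is a subset of *A*, so with *n* patients in the arm

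|C|/n ≤ |A|/n.

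The two are equal only if every patient with any event also had a collected one. Reported incidence can therefore only equal or understate overall incidence. Section 10.1 plans *n* = 70 eligible patients per randomized arm, so each patient whose events all fall outside collection lowers the figure by 1/70 = 0.0143, or 1.4 percentage points. The documents give no rate from which to count such patients.

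**3. Knowledge of dose**

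No blinding is described. Section 5.1 has the assignment sent to study personnel. Section 5.2 gives five tablets daily in one arm and one in the other, and has investigators at affiliate and other non-UNMC sites prescribe the randomized dose. That investigators know the arm is an inference from these provisions, but a firm one.

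**4. What the between-arm test would compare**

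For non-fatal events of grade 3 or 4, to a first approximation,

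reported rate = true rate × probability of being called related.

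So the ratio of reported rates between arms equals the ratio of true rates times the ratio of attribution probabilities. If the true rates are equal, the reported ratio is the attribution ratio alone. The documents give neither term, so this shows a mechanism and not a size or direction.

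**The case against.** The strongest reply is that the protocol defines its safety terms narrowly. Section 9.1.1 defines a vitamin D related adverse event, 9.1.2 a vitamin D related serious one, and 6.1 states the restriction openly, for an over-the-counter agent whose toxicity 9.0 calls well characterized. Read with those definitions, 10.2.5 lacks only a qualifier. Safety is not among the stated objectives, and the one safety decision rule, the 10% stopping rule in 10.4.1, counts severe events directly related to vitamin D and so fits the collection. All-cause death is also covered, free of attribution, by overall survival.

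Much of this stands. A restricted table can be produced, so a reader who infers that no safety comparison is possible goes too far. It would also be wrong to infer that grade 5 is lost altogether or that no unrelated event is ever recorded, given 9.0, 9.1.2 and 9.2.2. The stopping rule is unaffected. Nothing in the documents shows that attribution has distorted the comparison, or which way it would.

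The reply does not rescue the wording. Section 10.2.5 does not invoke the narrow definitions. Section 9.1.1 carries no grade limit, so adopting it would still conflict with 6.1. A promise of overall toxicity by grade reads against a dataset that largely begins at grade 3. Overall survival is tested in each arm against a fixed 80% (10.2.4), not between arms, so it does not replace a table of early deaths by dose.

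**Conclusion.** The point holds as a mismatch between 10.2.5 and Sections 6.1, 7.0 and 9.0. Overall adverse event incidence and a full toxicity-by-grade comparison cannot be obtained from the planned collection. Related events of grade 3 or higher, related SAEs and 30-day deaths can be tabulated. A report using the present wording would understate incidence by an amount the documents do not allow one to calculate.

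This assumes that sites collect what 6.1, 7.0 and 9.0 specify and no more. The attribution point further assumes that investigators know the dose, which is inferred from 5.1 and 5.2 and not stated. The issue is minor in that the primary progression-free survival analysis and the stopping rule do not depend on it, but the safety paragraph is wrong as written.

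**What to change.** 1. Restate 10.2.5 as the incidence, by randomized arm, of investigator-attributed vitamin D related events of grade 3 or higher, including grade 5, and of related SAEs.
2. Delete the sentence on overall toxicity by grade.
3. Reconcile grade 3 and 4 in 6.1 and 9.0 with grade 3 or higher elsewhere in 9.0 and in 9.2.2.
4. Tabulate by arm the deaths within 30 days of study treatment that 9.0 already requires to be reported regardless of relationship. This gives one comparison that does not pass through attribution.
5. State in the plan and the report that attribution was made with knowledge of dose.

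The cost is wording and one small table. Section 9.0 routes the 30-day deaths to the DSMC and does not say that they enter the study database, so that should be confirmed. The safety claim becomes narrower, covering attributed severe or serious events and not overall tolerability. Widening collection to all grades and causes is the alternative, but the listed protocol versions run from 2015 to December 2023, and events not recorded in that time may not be recoverable.

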10.3 Evaluable Patient

Histologically confirmed disease.

No premature discontinuation before completion of vitamin D cycles for reasons other than disease progression, starting new therapies, death, or study drug related unacceptable toxicity.

10.4 Stopping Rules

10.4.1 Interim Analyses

One interim monitoring analysis for efficacy will be conducted after n=35 patients in each randomized arm (35 patients in the low dose group and 35 patients in the high dose group) have enrolled. Two separate tests will be conducted to compare 1- the PFS in the low dose arm to the fixed expected value of 45% and 2- the PFS in the high dose arm to the fixed expected value of 45%. We will use an O'Brien-Fleming-type spending function to assess whether the interim results are sufficient to conclude that vitamin D supplementation in either the low dose or high dose arm is effective in increasing the PFS to 60%. The monitoring boundary p-values associated with the 1 interim look using the O'Brien-Fleming spending function will be 0.001525 with the final analysis being done with p=0.024501. The type I error associated with this monitoring plan is approximately 0.025. If $\geq 10\%$ of patients in either Vitamin D arm has severe adverse events that are felt to be directly related to the Vitamin D supplement, the study will be stopped.

Section 11.0 Records to Be Kept:

11.1 Quality Assurance

Complete records must be maintained in a research chart on each patient treated on the protocol. These records should include primary documentation (e.g., lab report slips, X-ray reports, scan reports, pathology reports, physician notes, etc.) which confirm that:

- The patient met the eligibility criteria.
- Signed informed consent was obtained prior to treatment.
- Treatment was given according to protocol (dated notes about doses given and reasons for any dose modifications).
- Toxicity was assessed according to protocol (laboratory report slips, etc.).
- Response was assessed according to protocol (x-ray, scan, lab reports, dated notes on measurements & clinical assessment, as appropriate).

11.2 Electronic Data Capturing (EDC) System

Data will be stored electronically for this study in the Advarra EDC system contained on the company's secure server. Data forms will not differ from the paper versions with the exception of an electronic format containing the UNMC Fred & Pamela Buffett Cancer Center and Advarra logo.

Advarra EDC provides for remote data collection that meets FDA 21 CFR Part 11 requirements as well as HIPAA and other regulatory requirements designed to enhance data security and protect patient confidentiality. Authorized users log into Advarra through a secure connection and must provide a valid username, password, and database ID. This data may be made available to the public at large.

Section 12.0 Patient Consent Form Statement:

12.1 Human Subjects Research Protection Training

All personnel involved in this research project will have completed the OHRP-approved computer based training course on the Protection of Human Research Subjects. All clinical and correlative research included in this application will have approval by the institutional review board.

12.2 Study Population

Subjects are from all socio-economic groups and will be entered into the study without bias with respect to gender or race. Attempts will be made to recruit minorities. No vulnerable subjects will be included in the study.

12.3 Recruitment and Informed Consent

Subjects with an initial diagnosis of cancer seen and evaluated at IRB approved sites will be available for recruitment. These subjects will be informed of the nature of this study, and will be asked to participate on a voluntary basis after informing them of the possible risks and benefits of the study. A number of public registries may be accessible to health care providers and prospective subjects as listed below.

National Library of Medicine – NCT02553447; <http://clinicaltrials.gov> ()

National Cancer Institute – NCI-2015-01502; <http://www.cancer.gov> ()

12.4 Subject Competency

Subjects will be eligible to participate in the study only if they are competent to give informed consent. A subject that the investigator judges to be incompetent will not be enrolled.

12.5 Process of Informed Consent

If the patient chooses to be participate in this study, informed consent will be obtained by the investigators. The study and procedures involved, including the risks, will be explained in detail

to each subject. It will be clearly explained to the subject that this is a research study and that participation is entirely on a voluntary basis. Subjects will be given the option to discuss the study with a family member, friend, counselor or, another physician. The participating investigators will be available to discuss the study with them.

12.6 Subject/Representative Comprehension

When the process of informed consent is completed, the subject will be asked to state in his/her own words, the purpose of the study, the procedures that will be carried out, potential risks, potential benefits to the subject, the alternatives and the right to withdraw from the study. If there is any indication that a given subject's comprehension is anything less than accurate, the points of confusion will be discussed and clarified.

12.7 Information Purposely Withheld

The results of the tests done solely for research purposes will not be disclosed to the subject. No other information will be purposely withheld from the subject.

12.8 Potential Benefits of the Proposed Research to the Subjects

Normal Vitamin D levels are associated with improved bone health and possibly improved progression-free and overall survival in patients with NHL and CLL.

12.9 Potential Benefits to Society.

Information obtained from this study may help other patients by contributing to the knowledge of the biology of cancers, and to understand the potential clinical benefit of this regimen.

12.10 Potential Risks

A rare but potential harm of treatment with oral vitamin D is toxicity, which may lead to hypercalcemia, hyperphosphatemia, suppressed parathyroid hormone, and hypercalciuria. However, the 25-(OH) D level associated with toxicity (often defined as >500 nmol/L [>200 ng/mL]) is well above the level considered to be sufficient. Treatment with vitamin D plus calcium may also be associated with increased risk for kidney stones; vitamin D alone does not seem to increase this risk. It is believed the treatment option outlined in the study will not pose significant additional risks compared to conventional treatment.

12.11 Therapeutic Alternatives

If subjects choose not to participate in this study, they may elect to receive standard therapy as per their primary oncologist, which may include no evaluation of vitamin level in the oncology setting and/or treatment recommendations that may or may not be similar to treatment as described in this protocol per individual practitioner.

Appendix A: Eligibility checklist

Date Completed:	IRB# 556-15 Title: A Pilot Study of Vitamin D Replacement in Patients with Non-Hodgkin's Lymphoma or Chronic Lymphocytic Leukemia with Low Vitamin D Levels PI: [name]		Checklist Version # 6.X Dated: XXMmmYYYY		
Site:					
Subject ID#:	Subject Initials:		Waiver #:		
Inclusion Criteria: Response should be YES			Yes	No	NA
1. Histologically confirmed newly diagnosed or previously untreated Non-Hodgkin's Lymphoma or CLL (Subjects may be under no treatment "wait and watch" OR have received two cycles of chemotherapy or localized radiation therapy before informed consent.)					
2. 18 years of age or older (19 years or older in Nebraska).					
3. Serum 25-hydroxyvitamin D [25(OH) D] drawn at time of enrollment (NOTE: Subjects currently taking < 1000 IU/day Vitamin D supplements are eligible for screening.)					
4. Simultaneous participation in other therapeutic clinical trials will be allowed.					
5. Subject must be aware of the neoplastic nature of his/her disease and willingly provide written, informed consent after being informed of the procedure to be followed, the nature of the therapy, alternatives, potential benefits, side-effects, risks, and discomforts.					
Exclusion Criteria: Response should be NO			Yes	No	NA
1. History of uncontrollable allergic reactions to vitamin D.					
2. Currently taking vitamin D supplement \geq 1000 IU/day.					
3. History of Paget's disease.					
4. Hypercalcemia					
5. Any other clinically significant medical disease or condition, laboratory abnormality, or psychiatric illness that, in the Investigator's opinion, may interfere with protocol adherence or a subject's ability to give informed consent.					
6. Inability to cooperate with the requirements of the protocol.					
All questions regarding eligibility for potential subjects should be directed to the UNMC IIT Office at [contact].					

 Subject satisfies all criteria.	
Eligibility:	 Subject not formally eligible, but admitted to this study because (state reason):
ELIGIBILITY reviewed and confirmed. (Reviewer - Study Nurse Coordinator(s) or PI designee)	
Reviewer Signature _____	Date _____
Printed Name of Reviewer: _____	

